#### 4.6.1.2 Neutralizing antibody responses

Elicitation of neutralizing antibody responses was tested using the TZM-bl assay [26,27] and PBMC assay [28,29]. The TZM-bl assay provides a well-validated, high-throughput assessment of plasma inhibition of entry into a laboratory cell line. The PBMC neutralization provides a dose-response measure of plasma antibody inhibition of infectious molecular clones expressing luciferase reporters in a 72 hour culture of stimulated primary blood mononuclear cells. In the TZM-bl assay, sera from vaccinated rabbits neutralized 3 of 6 viruses, reflecting a predominantly Tier 1 (easy to neutralize) response. There was no neutralizing activity against the homologous CO6980 pseudovirus (Tier 2) or heterologous Tier 2 CRF01\_AE viruses (Figure 4-4 A, C). In the PBMC assay, neutralization was seen against 5 tested viruses, including the homologous CO6980 strain (Figure 4-4 B, D).

#### 4.6.2 Immunogenicity of gp145 C.6980 in rabbits, study #2: fractionated protein

[figure not shown]
In Study 2, rabbits were immunized with either unfractionated gp145 C.6980 or preparations enriched for dimers, trimers, or other higher order fractions based on size-exclusion chromatography (see Figure 4-1A). Sera were tested for binding and neutralizing antibody responses.

#### 4.6.2.1 Binding antibody responses

Sera were collected 2 weeks after the last vaccination (week 10) and tested for binding activity to homologous and heterologous Envs (clade C gp120, subtype C gp140, and cyclic V2 peptides of the homologous CO6980.v0.c22 strain). Responses in sera from animals vaccinated with unfractionated gp145 C.6980 were similar to the responses seen in Study 1. Sera from animals vaccinated with purified fractions displayed similar profiles as the unfractionated animals in Study 1 and 2.

#### 4.6.2.2 Neutralizing antibody responses

As in Study 1, elicitation of neutralizing antibody responses was tested in the TZM-bl assay and PBMC assay. Sera from vaccinated rabbits were tested against the 3 heterologous pseudoviruses that were neutralized in Study 1 and the homologous C.6980 pseudovirus. Neutralization activity was seen for the 3 heterologous Tier 1 viruses and was not different between the unfractionated and purified proteins. As in Study 1, neutralizing activity was seen against all 4 viruses in the PBMC assay. Thus, unfractionated and each oligomeric formulation elicited Tier 1 neutralizing antibody responses.

**Figure 4-4** Fractionated and unfractionated gp145 C.6980 induce heterologous Tier 1 neutralizing antibody responses. Neutralizing antibody responses detected by TZM-bl (A and C) and PBMC assays (B and D). In Study 1, neutralization in TZM-bl assay is seen against Tier 1 viruses only in the TZM-bl assay (A) and more widely in the PBMC assay (B). In Study 2, similar titers are seen with fractionated and unfractionated gp145 C.6980 against Tier 1 viruses (C and D).

#### 4.6.3 Preclinical study of gp145 C.6980 in non-human primates

gp145 C.6980 was administered to 16 Indian-origin rhesus macaques three times over a period of nine months in conjunction with recombinant live attenuated modified vaccinia Ankara (MVA) vector encoding HIV-1 GagPol/Env derived from subtypes A, C, and E. Animals received MVA at month 0, followed by

concurrent MVA and gp145 at months 3, 6, and 12. gp145 C.6980 immunizations consisted of 100 mcg of protein adjuvanted with aluminum hydroxide (Alhydrogel, Brenntag) delivered IM. The protein was safely administered and well-tolerated with no adverse events. Animal body weights and temperatures remained stable following each immunization. gp145 C.6980 was immunogenic in all animals, eliciting binding antibody responses with a median titer of  $10^5$  to gp140 (subtype C CN54) and  $10^{3.7}$  to cyclic V2 peptide (gp145). Tier 1 neutralizing antibodies were also consistently observed, showing a median ID50 of  $10^3$  to both MW965 and TH023 (subtype C and E, respectively). gp120-specific CD4+ T cells were observed in most animals, ranging from 0.1-0.5% of the memory compartment, while CD8+ T-cell responses were observed in only a subset of animals at 0.6-3% of memory cells. In sum, gp145 C.6980 showed consistent and robust immunogenicity with no safety concerns in nonhuman primates.

#### 4.7 Clinical studies

Though gp145 C.6980 has not previously been evaluated in humans, the safety of other HIV Env proteins administered with alum has been extensively studied in clinical and preclinical studies. The extensive clinical experience with these HIV Envs as vaccine antigens is described briefly here.

Multiple monomeric Env proteins (gp120, gp140, gp145, gp160) have been administered in many clinical trials as the sole vaccine component or as a part of a prime boost regimen. The majority of proteins were produced in CHO cells (as is gp145 C.6980). Overall, vaccines consisting of or expressing HIV Env variants were well tolerated. The long-term safety data from NIAID-sponsored clinical trials conducted between 1987 and 2001 was analyzed by Gilbert and colleagues [30]. This report included 51 phase 1 and 2 trials, including data on 3189 uninfected participants; the majority of studies included an Env protein as an immunogen [30]. The published analysis concluded that 1 vaccine containing a C4-V3 polypeptide vaccine emulsified in incomplete Freund's adjuvant caused serious toxicity, but otherwise no serious safety problems were identified for any of the vaccines or adjuvants studied.

The largest clinical safety dataset for Env proteins is from the VAX003, VAX004, and RV144 studies, in which more than 12,000 participants received either AIDSVAX B/E or AIDSVAX B/B (each a mixture of 2 CHO-derived gp120 proteins totaling 600mcg [300mcg of each protein] in alum adjuvant). Safety data showed that these vaccines appeared safe and well tolerated [31]. In the RV144 trial, the frequency of reactions in AIDSVAX B/E recipients was 54.6% vs. 46.3% in placebo recipients. Pain and tenderness were the most frequent local reactions observed, and all reactions were generally mild and resolved within 3 days. Systemic reactogenicity was also observed more frequently in the combined vaccine group (77.2%) than the placebo group (59.8%). Systemic reactions following the third and fourth vaccination could not be attributed to a specific vaccine (ie, AIDSVAX or ALVAC).

Recent clinical experience with other oligomeric Env antigens is also available from a smaller number of studies. Oligomeric forms of gp140 clade C and clade B Env proteins manufactured by Novartis Vaccines and Diagnostics have been evaluated in 3 IND studies (clade C gp140 strain TV1 with MF59 and clade B gp140 strain SF162 with MF59) [32,33]. An oligomeric gp160 Env protein was administered to 45 participants in RV132, a phase 1-2 prime-boost study in Thailand [34]. More than 100 participants received the oligomeric subtype C product in a recent HVTN study (HVTN 086) [35]. The safety profile of these products was similar to that observed for the AIDSVAX products. The vaccines were generally well tolerated without vaccine-related serious adverse events.

#### 4.8 Potential risks of study products and administration

**Table 4-2 Summary of potential risks of study products and administration**

Common	
 
• Mild to moderate injection site pain, tenderness, erythema, or swelling/induration/edema
 
• Malaise/fatigue, myalgia, or headache in the first few days following injection
 
• A vaccine-induced positive HIV antibody test result
 

Less common	
 
• Severe injection site pain or tenderness
 
• Fever, chills, flu-like syndrome, arthralgia, rash, nausea, or dizziness in the first few days following injection
 
• Vasovagal reaction/lightheadedness/dizziness related to the injection procedure
 
• Transient changes in clinical laboratory values
 
• Injection site hematoma, bruising/ecchymosis, other transient lesions, itching, or bleeding related to the injection procedure
 

Uncommon or rare	
 
• Severe localized injection site reaction, such as sterile abscess or secondary bacterial infection
 
• Allergic reaction, including rash, urticaria, angioedema, bronchospasm, or anaphylaxis
 
• Muscle damage at the injection site
 

Theoretical risks	
 
• Autoimmune disease
 
• Effects on a participant's response to an approved HIV vaccine administered in the future
 
• Effects on susceptibility to HIV, if the participant is exposed to HIV
 
• Effects on the course of HIV infection/disease, if the participant is infected with HIV
 
• Effects on the fetus and on pregnancy
 

## 5 Objectives and endpoints

### 5.1 Primary objectives and endpoints

*Primary objective 1:*

To evaluate the safety and tolerability of 1 injection of gp145 C.6980 at 2 dose levels with alum adjuvant in HIV-seronegative low risk adults

*Primary endpoints 1:*

Frequency of severe local and systemic reactogenicity signs and symptoms: pain, tenderness, maximum severity of pain and/or tenderness, erythema, induration, fever, malaise/fatigue, myalgia, headache, nausea, vomiting, chills, arthralgia, maximum severity of systemic symptoms (graded using the Division of AIDS Table for Grading the Severity of Adult and Pediatric Adverse Events. Corrected Version 2.1, dated July 2017)

Frequency of AEs by treatment arm, by body system, Medical Dictionary for Regulatory Activities (MedDRA) preferred term, severity, and assessed relationship to study products (graded using the Division of AIDS Table for Grading the Severity of Adult and Pediatric Adverse Events. Corrected Version 2.1, dated July 2017)

Serious adverse events (SAEs) throughout the active surveillance period

Laboratory measures of safety: white blood cells (WBC), neutrophils, lymphocytes, hemoglobin, platelets, ALT, and creatinine at baseline and following vaccinations, by treatment arm (graded using the Division of AIDS Table for Grading the Severity of Adult and Pediatric Adverse Events. Corrected Version 2.1, dated July 2017)

### 5.2 Secondary objectives and endpoints

*Secondary objective 1:*

To evaluate the safety and tolerability of 3 injections of gp145 C.6980 at 2 dose levels with alum adjuvant in HIV-seronegative low risk adults

*Secondary endpoints 1:*

Frequency of severe local and systemic reactogenicity signs and symptoms: pain, tenderness, maximum severity of pain and/or tenderness, erythema, induration, fever, malaise/fatigue, myalgia, headache, nausea, vomiting, chills, arthralgia, maximum severity of systemic symptoms (graded using the Division of AIDS Table for Grading the Severity of Adult and Pediatric Adverse Events. Corrected Version 2.1, dated July 2017)

Frequency of AEs by treatment arm, by body system, Medical Dictionary for Regulatory Activities (MedDRA) preferred term, severity, and assessed relationship to study products (graded using the Division of AIDS Table for Grading the Severity of Adult and Pediatric Adverse Events. Corrected Version 2.1, dated July 2017)

SAEs throughout the active surveillance period

Laboratory measures of safety: white blood cells (WBC), neutrophils, lymphocytes, hemoglobin, platelets, ALT, and creatinine at baseline and following vaccinations, by treatment arm (graded using the Division of AIDS Table for Grading the Severity of Adult and Pediatric Adverse Events. Corrected Version 2.1, dated July 2017)

*Secondary objective 2:*

To characterize the immunogenicity of 1 injection of gp145 C.6980 at 2 dose levels with alum adjuvant in HIV-seronegative low risk adults

*Secondary endpoints 2:*

Response rates and levels of vaccine-induced binding antibodies to HIV proteins measured by the binding antibody multiplex assay (BAMA) at 2 weeks following the first vaccination

*Secondary objective 3*

To characterize the immunogenicity of 3 injections of gp145 C.6980 at 2 dose levels with alum adjuvant in HIV-seronegative low risk adults

*Secondary endpoints 3:*

Response rates and levels of vaccine-induced binding antibodies to HIV proteins measured by the BAMA at 2 weeks following the third vaccination

Response rates and levels of CD4+ and CD8+ T cells measured by intracellular cytokine staining (ICS) at 2 weeks following the third vaccination

Response rates and levels of neutralizing antibody responses against HIV-1 isolates at 2 weeks following the third vaccination

### **5.3 Exploratory objectives**

*Exploratory objective 1:*

To describe participants' baseline characteristics (eg, previous exposure to vaccinia) and their impact on vaccine-induced immune responses

*Exploratory objective 2:*

To determine the frequency of circulating Tfh, Tfr, and plasmablasts in response to each vaccination regimen

*Exploratory objective 3:*

To further evaluate immunogenicity of each vaccine regimen, additional immunogenicity assays may be performed, including on samples from other timepoints, based on the HVTN Laboratory Assay Algorithm.

*Exploratory objective 4:*

To conduct analyses related to furthering the understanding of HIV, immunology, vaccines, and clinical trial conduct.

## 6 Statistical considerations

### 6.1 Accrual and sample size calculations

Recruitment will target enrolling 45 healthy, HIV-uninfected adult participants aged 18 to 50 years, at low risk for HIV infection: 40 vaccine and 5 placebo recipients. Each participant will be randomly assigned to receive 1 of 2 doses of the vaccine regimen or placebo in a 5:3:1 ratio with 25, 15, and 5 participants in the 300 mcg dose (Group 1), 100 mcg dose (Group 2) and placebo (Group 3) arms, respectively. Since the 300 mcg dose level will be considered in future China CDC/NIAID/HVTN collaborative trials, the sample size of Group 1 accounts for the minimal sample size requirement ( $\geq 20$ ) by China FDA to generate safety data for exporting the vaccine to China. The placebo arm provides a control group for assay quality assurance and blinding.

To ensure that both men and women will be adequately represented in the trial, the trial will enroll at least approximately 40% of each sex assigned at birth overall. Hence, when approximately 18 participants of 1 sex are enrolled, sites will be notified to stop further recruitment of persons of that sex assigned at birth.

Since enrollment is concurrent with receiving the first study vaccination, all participants will provide some safety data. However, for immunogenicity analyses, it is possible that data may be missing for various reasons, such as participants terminating from the study early, problems in shipping specimens, low cell viability of processed PBMCs, or high assay background levels. Immunogenicity data from 17 phase 1 and 2 phase 2a HVTN vaccine trials, which began enrolling after June 2005 (data as of September 2014), indicate that 10% is a reasonable estimate for the rate of missing data at days 14 and 182. For this reason, the sample size calculations in Section 6.1.2 account for 4 enrolled participants having missing data for the primary immunogenicity endpoint.

#### 6.1.1 Sample size calculations for safety

The goal of the safety evaluation for this study is to identify safety concerns associated with product administration. The ability of the study to detect SAEs can be expressed by the true event rate above which at least 1 SAE would likely be observed and the true event rate below which no events would likely be observed. Specifically, for each vaccine arm of the study ( $n = 15, 25$ ), there is a 90% chance of observing at least 1 event if the true rate of such an event is 14.3% or 8.9% or more, respectively; and there is a 90% chance of observing no events if the true rate is 0.4% or 0.7% less, respectively. For vaccine arms combined ( $n = 40$ ), there is a 90% chance of observing at least 1 event if the true rate of such an event is 5.6% or more; and there is a 90% chance of observing no events if the true rate is 0.26% or less. As a reference, in previous AVEG HIV vaccine trials, 3.5% of control participants experienced an SAE; in HVTN vaccine trials from December 2000 through April 2014, about 4% of participants who received placebos experienced an SAE.

Probabilities of observing 0 and 2 or more events among 15, 25, or 40 vaccine recipients are presented in [Table 6-1](#) below for a range of possible true AE rates. These calculations provide a complete picture of the sensitivity of this study design to identify potential safety problems with the vaccine. For example, we see that if the true rate of AEs is 1%, there is an 86%, 78%, or 67% chance that no events will be observed in the vaccine arm of 15, 25, or 40 participants, respectively.

**Table 6-1 Probability of observing 0 events, 1 or more events, and 2 or more events, among n=15, 25 or 40 vaccine recipients, for different true event rates**

True event rate (%)	Pr(0/15)	Pr(2+/15)	Pr(0/25)	Pr(2+/25)	Pr(0/40)	Pr(2+/40)
1	0.860	0.010	0.778	0.026	0.669	0.061
3.5	0.586	0.095	0.410	0.218	0.240	0.411
5	0.463	0.171	0.277	0.358	0.129	0.601
10	0.206	0.451	0.072	0.729	0.015	0.920
20	0.035	0.833	0.004	0.973	<0.001	0.999
30	0.005	0.965	<0.001	0.998	<0.001	>0.999
40	<0.001	0.995	<0.001	>0.999	<0.001	<0.999

An alternative way of describing the statistical properties of the study design is in terms of the 95% confidence interval (CI) for the true rate of an AE based on the observed data. [Table 6-2](#) shows the 2-sided 95% CIs for the probability of an event based on a particular observed rate. Calculations are done using the score test method [36]. If none of the 15, 25 or 40 vaccine recipients experience a safety event, the 95% 2-sided upper confidence bound for the true rate of such events is 21.8%, 13.7% or 8.81%, respectively.

**Table 6-2 Two-sided 95% confidence intervals based on observing a particular rate of safety endpoints for arms of size n1 and n2**

Observed event rate	CI (%)
0/15	(0.00, 21.8)
1/15	(0.17, 31.9)
2/15	(1.66, 40.5)
0/25	(0.00, 13.7)
1/25	(0.10, 20.4)
2/25	(0.98, 26.0)
0/40	(0.00, 8.81)
1/40	(0.06, 13.2)
2/40	(0.61, 16.9)

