### 6.1.2 Sample size calculations for immunogenicity

The main goals of this trial regarding immunogenicity outcomes involve a preliminary estimation of response rates based on data from the BAMA, ICS, and nAb assays among vaccinees at 2 weeks following vaccination. No adjustment for multiple comparisons will be made for the use of multiple assays. The precision with which the true response rate can be estimated from the observed data depends on the true underlying response rate and the sample size. Two-sided 95%

confidence intervals for the response rate based on observing a particular rate of responses in the vaccinees is shown in [Table 6-3](#). Calculations are done using the score test method [36]. The n = 13, 22, 36 assumes a 10% rate of missing immunogenicity data.

**Table 6-3 Two-sided 95% confidence intervals for the true response rate based on observing a particular rate of responses in the vaccinees (n = 13, 22, 36)**

No. of responses	Observed response rate (%)	CI
n = 13		
3/13	23.1	[8.2, 50.2]
5/13	38.5	[17.7, 64.5]
7/13	53.8	[29.1, 76.8]
11/13	84.6	[57.8, 95.7]
12/13	92.3	[66.7, 98.6]
n = 22		
3/22	13.6	[4.8, 33.3]
5/22	22.7	[10.1, 43.4]
7/22	31.8	[16.4, 52.7]
11/22	50.0	[30.7, 69.3]
15/22	68.2	[47.3, 83.6]
19/22	86.4	[66.7, 95.3]
20/22	90.9	[72.2, 97.5]
n = 36		
3/36	8.3	[2.9, 21.8]
5/36	13.9	[6.1, 28.7]
7/36	19.4	[9.8, 35]
11/36	30.6	[18, 46.9]
15/36	41.7	[27.1, 57.8]
19/36	52.8	[37, 68]
23/36	63.9	[47.6, 77.5]
27/36	75	[58.9, 86.2]
33/36	91.7	[78.2, 97.1]

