An alternative way of describing the statistical properties of the study design is in terms of the 95% confidence interval (CI) for the true rate of an AE based on the observed data. Table 2 (same as Table 6-2 in the Protocol) shows the 2-sided 95% CIs for the probability of an event based on a particular observed rate. Calculations are done using the score test method [36]. If none of the 15, 25 or 40 vaccine recipients experience a safety event, the 95% 2-sided upper confidence bound for the true rate of such events is 21.8%, 13.7% or 8.81%, respectively.

Table 2: Two-sided 95% confidence intervals based on observing a particular rate of safety endpoints for arms of size n_1 and n_2

Observed event rate	CI (%)
0/15	(0.00, 21.8)
1/15	(0.17, 31.9)
2/15	(1.66, 40.5)
0/25	(0.00, 13.7)
1/25	(0.10, 20.4)
2/25	(0.98, 26.0)
0/40	(0.00, 8.81)
1/40	(0.06, 13.2)
2/40	(0.61, 16.9)

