10.5 Immunogenicity analysis

10.5.1 General approach

For the statistical analysis of immunogenicity endpoints, data from enrolled participants will be used according to the initial randomization assignment regardless of how many injections they received. Additional analyses may be performed, limited to participants who received all scheduled injections per protocol. Assay results that are unreliable, from specimens collected outside of the visit window, or from HIV-infected participants postinfection are excluded. Since the exact date of HIV infection is unknown, any assay data from blood draws 4 weeks prior to an infected participant's last seronegative sample and thereafter may be excluded. If an HIV-infected participant does not have a seronegative sample postenrollment, then all data from that participant may be excluded from the analysis.

Discrete categorical assay endpoints (eg, response rates) will be analyzed by tabulating the frequency of positive response for each assay by antigen and treatment arm at each timepoint for which an assessment is performed. Crude response rates will be presented with their corresponding 95% confidence interval estimates calculated using the score test method [1]. Because of the small numbers of control participants, no adjustment will be made to the vaccine arm estimates for the false positive rates in the control arms. Barnard or Fisher's exact tests, as specified in the SAP, will be used to compare the response rates of the 2 vaccine arms, with a significant difference declared if the 2-sided p-value is ≤ 0.05 . In general Barnard's is preferred since under most circumstances it is more powerful than Fisher's [2].

For quantitative assay data (eg, IgG binding Ab response from the multiplex assay or CD4⁺/CD8⁺ T cell response from the ICS assay), graphical and tabular summaries of the distributions by antigen, treatment arm, and timepoint will be made. For all primary and secondary immunogenicity endpoints, box plots and plots of estimated reverse cumulative distribution curves will be used for graphical display of all of the study arms. Typically the results will be shown for each vaccine arm and for the control arm separately.

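### Protocol 6.1.1 and SAP 9 give the two no-event rates in reverse order, label exact intervals as score intervals, and print one table cell with the wrong inequality sign

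*Protocol*

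**What the plan says.** Protocol 6.1.1 describes what the safety sample can show. It sets the order of the arms with "for each vaccine arm of the study ( $n = 15, 25$ ), there is a 90% chance of observing at least 1 event", gives 14.3% and 8.9% as the corresponding rates, and continues "there is a 90% chance of observing no events if the true rate is 0.4% or 0.7% less, respectively". For the 40 vaccinees combined it gives 5.6% for at least one event and 0.26% for none.

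Table 6-1 is captioned "Probability of observing 0 events, 1 or more events, and 2 or more events, among n=15, 25 or 40 vaccine recipients". Its last row (true rate 40%) prints `<0.999` for two or more events among 40. The row above (30%) prints `>0.999`.

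Table 6-2 gives two-sided 95% intervals for 0, 1 and 2 events among 15, 25 and 40. The method statement is "Calculations are done using the score test method [36]. If none of the 15, 25 or 40 vaccine recipients experience a safety event", after which the zero-event upper bounds follow. Protocol 6.1.2 attaches the same method statement to Table 6-3: "Calculations are done using the score test method [36]. The n = 13, 22, 36 assumes a 10% rate of missing immunogenicity data".

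SAP 9 repeats the no-event sentence, the `<0.999` cell, the method label and the bounds: "the 95% 2-sided upper confidence bound for the true rate of such events is 21.8%, 13.7% or 8.81%, respectively".

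**The concern.** The no-event rates fail a check that needs no calculation. The larger the arm, the lower the true rate must be to keep a 90% chance of seeing nothing. The printed rates run 0.4% (n = 15), 0.7% (n = 25), 0.26% (n = 40), which is not monotone. The at-least-one-event rates in the same sentence are in the right order, so no other reading of the arm order rescues it.

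The zero-event bounds in Table 6-2 are higher than score bounds for these sample sizes, although Table 6-3, under the same label, looks like a score table. The last cell of Table 6-1 has a probability falling as the event rate rises, which cannot happen.

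Safety is the primary objective, and this section is where the protocol quantifies what 15, 25 and 40 vaccinees can show about it. A wrong property for the 300 mcg arm, and a table that cannot be reproduced by its named method, should not stay in that section or be carried into the SAP.

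**Working it through.** **Inputs.** Arm sizes 15, 25 and 40, the 90% target, and the tables, all from protocol 6.1.1 and 6.1.2 (SAP 9 carries the same safety figures). Events are treated as independent binomial.

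**1. Rates for at least one event and for no events**

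At least one event with 90% probability: p = 1 − 0.1^(1/n). No events with 90% probability: p = 1 − 0.9^(1/n).

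| n | At least one: exact | Printed | Probability at printed rate | No event: exact | Printed | Probability at printed rate |
|---|---|---|---|---|---|---|
| 15 | 14.23% | 14.3% | 90.1% | 0.700% | 0.4% | 0.996^15 = 94.2% |
| 25 | 8.80% | 8.9% | 90.3% | 0.421% | 0.7% | 0.993^25 = 83.9% |
| 40 | 5.59% | 5.6% | 90.0% | 0.263% | 0.26% | 0.9974^40 = 90.1% |

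The at-least-one statements hold, and so does the n = 40 no-event statement. The two single-arm no-event rates do not match their arms. Exchanged, they do: 0.993^15 = 90.0% and 0.996^25 = 90.5%.

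**2. Table 6-2**

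With zero events the two-sided 95% upper bounds have closed forms: exact (Clopper-Pearson) 1 − 0.025^(1/n), and score (Wilson) z²/(n + z²) with z² = 3.8415.

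| n | Printed | Exact | Score | Printed − score (points) |
|---|---|---|---|---|
| 15 | 21.8% | 21.80% | 3.8415/18.8415 = 20.39% | 1.4 |
| 25 | 13.7% | 13.72% | 3.8415/28.8415 = 13.32% | 0.4 |
| 40 | 8.81% | 8.81% | 3.8415/43.8415 = 8.76% | 0.05 |

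The rows with events:

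| Events | Printed | Exact | Score |
|---|---|---|---|
| 1/15 | 0.17, 31.9 | 0.17, 31.95 | 1.19, 29.82 |
| 2/15 | 1.66, 40.5 | 1.66, 40.46 | 3.74, 37.88 |
| 1/25 | 0.10, 20.4 | 0.10, 20.35 | 0.71, 19.54 |
| 2/25 | 0.98, 26.0 | 0.98, 26.03 | 2.22, 24.97 |
| 1/40 | 0.06, 13.2 | 0.06, 13.16 | 0.44, 12.88 |
| 2/40 | 0.61, 16.9 | 0.61, 16.92 | 1.38, 16.50 |

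All nine rows agree with the exact interval to the printed digits. None of the 15 non-zero limits agrees with the score interval. Continuity-corrected Wilson, Agresti-Coull, Jeffreys and Wald intervals were also tried, and none fits.

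Table 6-3, under the same label, does reproduce as score: 19 of 21 rows match to the printed digit. The other two differ by less than 0.06 point at one limit (3/13 upper 50.26, printed 50.2; 3/22 lower 4.75, printed 4.8). The exact interval for 3/13 would be 5.0 to 53.8, against the printed 8.2 to 50.2. One label therefore covers two methods.

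**3. Table 6-1**

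Pr(0) = (1 − p)^n and Pr(2+) = 1 − (1 − p)^n − np(1 − p)^(n−1). Of the 42 cells, 41 reproduce. The exception is n = 40, p = 0.40:

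1 − 0.6^40 − 40 × 0.4 × 0.6^39 = 1 − 3.7 × 10⁻⁸ = 0.99999996

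This is printed `<0.999`. At 30% the value is 0.999988, correctly printed `>0.999`.

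**The case against.** The best case on the other side is that these are errata in descriptive text.

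- **Nothing depends on them.** Protocol 6.1 says "the sample size of Group 1 accounts for the minimal sample size requirement" of at least 20. The safety analyses (protocol 6.4.3, SAP 10.3) plan no confidence intervals, and adverse events are not formally compared between arms. This stands, and it limits the point to corrections of text and labels.
- **Only half of the reversed sentence is false in substance.** For n = 15 at 0.4% or below, the chance of no events is at least 94.2%, so that half is merely conservative. This stands. The n = 25 half remains false.
- **The rates in question are low.** Section 6.1.1 quotes background SAE rates of 3.5% and about 4%, far above 0.4% or 0.7%, and Table 6-1 gives correct no-event probabilities at 1% and above. True, but the sentence still states a property that the larger arm does not have.
- **The label may be right and the values wrong.** The score method is named elsewhere, including for response rates in protocol 6.4.4.1 and SAP 10.5.1. The documents do not show which was intended. What is established is that the label does not describe the numbers printed, so either may be changed.
- **The table cell is an obvious slip.** Yes, but it appears in both documents and takes one character to correct.

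**Conclusion.** All three errors are confirmed in both documents. The no-event rates are reversed: at 0.7% the 300 mcg arm has an 83.9% chance of no events, about 6 percentage points below the stated 90%. Table 6-2 and its zero-event bounds are valid exact intervals under a score label; the zero-event gap is 1.4, 0.4 and 0.05 points for n = 15, 25 and 40. Because the printed upper bounds are the higher ones, precision is not overstated. The `<0.999` cell is impossible.

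The results assume only independent binomial events and the plain Wilson form of the score interval, which is the form Table 6-3 follows. The point is worth correcting because it concerns the stated precision for the primary objective, but it changes no sample size, test or decision rule.

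**What to change.** In protocol 6.1.1 and SAP 9:

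1. Give the no-event rates as 0.7% for n = 15 and 0.4% for n = 25, and restore the missing word so that each reads as that rate or less.
2. Make Table 6-2 / SAP Table 2 and the zero-event bounds agree with their label, in one of two ways:
   - Relabel them as exact Clopper-Pearson and remove the score-method citation from that sentence in both documents; or
   - Keep the score label and replace the values: 0/15 (0, 20.4), 1/15 (1.19, 29.8), 2/15 (3.74, 37.9), 0/25 (0, 13.3), 1/25 (0.71, 19.5), 2/25 (2.22, 25.0), 0/40 (0, 8.76), 1/40 (0.44, 12.9), 2/40 (1.38, 16.5).

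   In either case SAP citation [36] must change, because the SAP reference list ends at 8. If the score method is kept, the SAP's own number for that source is 1, as in SAP 10.5.1. Leave the Table 6-3 label as it is.
3. In Table 6-1 / SAP Table 1, change `<0.999` to `>0.999`. While the table is open, note that its caption announces a probability of one or more events for which there is no column.

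The cost is a few text and label edits in two documents, with no change to design, sample size or analysis.
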